4.3. Analysis populations

The VITAL trial asses a model of HIV care in a "real-world" setting. The main interest is to assess effectiveness of the VITAL intervention, i.e. the degree of effect under "real-world" conditions. Accordingly, the ITT population is the analysis population of most relevance. Therefore, in the primary analysis, we will analyse participant outcomes in the cluster they were enrolled in, independent of their follow-up. As a sensitivity analysis we will conduct a per-protocol analysis

includes participants for whom the VITAL intervention was technically successful defined as all viral loads available in the VITALapp \leq 31 days after phlebotomy.

5. Trial population

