6.2. Analysis methods

General: Continuous variables will be inspected using histograms: 1) to assess for outliers which may be queried for accuracy, and 2) to assess whether appropriate transformations are required for the regression model. Outcomes will be summarized using medians and interquartile ranges for

continuous variables and numbers and percentages for categorical variables, by randomized group. Percentages will be reported to one decimal place. For the primary outcome and its sensitivity analyses, we will report adjusted odds ratios and adjusted risk differences derived from regression models. If a model fails to converge using the identity link function (for estimating the adjusted risk difference), only adjusted odds ratios will be reported. Methods for secondary analyses are detailed below; for secondary analyses aligned with the primary outcome analysis, we will report adjusted odds ratios. If the number of outcome events is insufficient to support reliable coefficient estimation (e.g., fewer than 10 events per parameter), no regression model will be fitted. We will consider the day of enrolment until the day of primary endpoint VL or until 28 months after enrolment if endpoint VL missing as study period for each participant.

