Time and motion studies are conducted to collect the costing data necessary to provide the intervention. All clinics contributed several time and motion observations. An experienced research assistant collects data on time required to complete each step of the intervention. Observing multiple visits allows estimation of the average time taken for each step. The time taken for research purposes (e.g. data collection) is noted separately from the estimated time needed for clinical services. In addition, interviews with study staff to quantify the effort required for each step of the intervention are conducted, as well as interviews with participants to assess opportunity costs. We also ask participants what expenses and opportunity costs they incurred while receiving the intervention. Furthermore, we collect data on the average cost of medical care in Lesotho associated with HIV infection and AIDS through literature review. A discount rate of 3% is used with sensitivity analysis of 0% to 5%.

Sensitivity analyses (primary outcome):

- Proportion of participants engaged in care (defined as documented visit attendance) with documented viral suppression (<1000 copies/mL) 24 months (16-28 months) after enrolment: The first sensitivity analysis assesses the robustness of the primary analysis to the primary endpoint definition by repeating the primary outcome analysis (ITT) with a VL cutoff modified to 1'000 copies/mL.
- 2. Proportion of participants engaged in care (defined as documented visit attendance) with documented viral suppression (<50 copies/mL) 24 months (16-28 months) after enrolment: The second sensitivity analysis assesses the robustness of the primary analysis to the primary endpoint definition by repeating the primary outcome analysis (ITT) with imputing the VLs of participants who were engaged in care but do not have a documented viral load at 24 months using the viral load history of the participants.
- 3. Proportion of participants engaged in care (defined as documented visit attendance) with documented viral suppression (<50 copies/mL) 24 months (16-28 months) after enrolment: The third sensitivity analysis assesses the robustness of the primary analysis to technical challenges with viral load result availability by repeating the primary outcome analysis in the per-protocol population defined as participants for whom all VL results were available in the VITALapp ≤31 days after phlebotomy during the study period.

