Secondary endpoints expressing supportive evidence:

- 9. Time to follow-up VL in case of an unsuppressed VL (≥ 50 copies/mL): This analysis will consider the time in weeks to follow-up VL in case of an unsuppressed VL (≥ 50 copies/mL) as outcome and use a multi-level linear regression model including clinic cluster as a random effect, arm allocation and the randomization stratification factor (district) as a fixed effect.
- 10. Time to ART regimen adaption in case of virologic failure: This analysis will consider the time in weeks to ART regimen adaption in case of virologic failure (defined as two consecutive VLs ≥1'000 copies/mL or three consecutive VLs ≥20 copies/mL from VITAL start 22.12.2022 and two consecutive VLs ≥50 copies/mL from 23.12.2022 − VITAL closure) as outcome and use a multi-level linear regression model including clinic cluster as a random effect, arm allocation and the randomization stratification factor (district) as a fixed effect.
- 11. Rate of clinic visits at 24 months after enrollment: This analysis will consider the number of clinic visits throughout the study period as outcome and use and use a multi-level Poisson regression model with offset study duration including clinic cluster as a random effect, arm allocation and the randomization stratification factor (district) as a fixed effect.
- 12. Proportion of participants with ART regimen modification due to virologic failure at 12 and 24 months among participants with virologic failure: This analysis will only include people with a virologic failure (defined as two consecutive VLs ≥1′000 copies/mL or three consecutive VLs ≥20 copies/mL from VITAL start 22.12.2022 and two consecutive VLs ≥50 copies/mL from 23.12.2022 VITAL closure). Then, this analysis will directly follow the primary endpoint analysis with endpoint ART modification.
- 13. **Proportion of participants having ever received TPT:** This analysis will directly follow the primary endpoint analysis with endpoint having ever received TPT by 24 months.

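### Sensitivity analysis 3 counts the endpoint viral load in its 31-day rule, so entry to the per-protocol set depends on the outcome and agreement with ITT cannot confirm non-inferiority

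*SAP*

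**What the plan says.** SAP 4.3 makes ITT the main population and adds: "As a sensitivity analysis we will conduct a per-protocol analysis". The set "includes participants for whom the VITAL intervention was technically successful defined as all viral loads available in the VITALapp" within 31 days of phlebotomy. The list of added sensitivity analyses in 6.1 and the footnote to Table 3 repeat the rule. Section 6.2 (sensitivity analysis 3) words it as "participants for whom all VL results were available in the VITALapp ≤31 days after phlebotomy during the study period" and gives the purpose: the analysis "assesses the robustness of the primary analysis to technical challenges with viral load result availability".

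The study period is defined at the start of 6.2. It runs from enrolment to the day of the endpoint VL, or "until 28 months after enrolment if endpoint VL missing as study period for each participant". The endpoint VL is thus one of the results that must be on time. Under the primary outcome in 6.2, a participant with no VL, or only an invalid one, in the window counts as a failure.

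Two other parts of 6.2 bear on how many VLs a person has. Endpoint 9 measures time to a follow-up VL after an unsuppressed one. Virologic failure (endpoints 10 and 12) requires repeated results, for example "two consecutive VLs ≥50 copies/mL from 23.12.2022".

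**The concern.** A per-protocol set should be defined by how the intervention was delivered, not by how the participant fared. Here the two are mixed. A success cannot exist without an endpoint VL, so every success must pass a timing test on that result. A failure through a missing endpoint VL has no such result to be late. A participant retested after an unsuppressed VL has more results, and one late result is enough for exclusion. The timing test on the endpoint VL also serves no purpose: once the sample is drawn, the speed of its return cannot change its value.

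This is the only per-protocol analysis in the plan, and from its layout Table 3 appears to apply the non-inferiority and superiority comparisons to it. Readers of a non-inferiority trial will look to it for support. If the set is selected on the outcome, and differently by arm, agreement or disagreement with ITT says little.

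**Working it through.** **The plan's own figure.** SAP 3.4 equates the margin, odds ratio (OR) 0.8, with 5% more failures at a 65% control success rate. Odds = 0.8 × 0.65/0.35 = 1.486; probability = 1.486/2.486 = 59.8%; difference 5.2 points. The stated 5% is reproduced. The SAP gives no number of VLs per person, no late rate and no split of failures into unsuppressed and missing, so all values below are assumptions. The arithmetic uses crude ORs and ignores clustering.

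**General formula.** Per-protocol OR = true OR × (retention of successes ÷ retention of failures, intervention) ÷ (the same ratio, control). If the two ratios are equal, they cancel: with the same rule, late rate, test counts and failure mix in both arms, 0.80 stays 0.80.

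**Step 1: the endpoint-VL condition alone.** Let q be the share of endpoint VLs that are late and s the share of failures with no endpoint VL. Successes are kept with probability 1 − q, failures with s + (1 − s)(1 − q). For q = 20%:
- s = 40%: 0.80/(0.40 + 0.60 × 0.80) = 0.80/0.88 = 0.91
- s = 80%: 0.80/(0.80 + 0.20 × 0.80) = 0.80/0.96 = 0.83

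If only the intervention arm is filtered, a true OR of 0.80 becomes 0.73 to 0.67. If both arms are filtered but 10% of results are late in control clinics, the control factor is 0.90/0.94 = 0.957 (s = 40%) or 0.90/0.98 = 0.918 (s = 80%). The OR becomes 0.80 × 0.909/0.957 = 0.76, or 0.80 × 0.833/0.918 = 0.73.

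**Step 2: adding the number of tests.** Let each result be on time with probability r, independently, so that a person with k results is kept with probability r^k. Let successes have 2 results. For a true OR of 0.80:

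| Scenario | r = 0.95 | r = 0.90 | r = 0.80 |
|---|---|---|---|
| A. Both arms filtered alike | 0.80 | 0.80 | 0.80 |
| B. Both filtered; all failures unsuppressed, with one more test in the intervention arm (factor 1/r) | 0.84 | 0.89 | 1.00 |
| C. Intervention only; all failures unsuppressed with 4 tests (r²/r⁴) | 0.89 | 0.99 | 1.25 |
| D. As C, but half of failures have no endpoint VL and 1 earlier test (r²/(0.5r + 0.5r⁴)) | 0.82 | 0.83 | 0.85 |
| E. As C, but all failures have no endpoint VL and 1 earlier test (r²/r) | 0.76 | 0.72 | 0.64 |

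For example, C at r = 0.80: 0.64/0.4096 = 1.5625, and 0.80 × 1.5625 = 1.25. Across the table the same true value lands anywhere from 0.64 to 1.25.

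**The case against.** Several points on the other side stand.

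- **No decision rests on this set.** Non-inferiority and superiority are decided in ITT (3.4, 6.1, 6.2), and the per-protocol analysis is labelled a sensitivity analysis with a technical purpose.
- **Selection on outcome alone does not bias the OR.** An arm difference is needed, and the SAP does not establish one. Sections 6.1 and 6.2 speak of participants without limiting the arm, so the plain reading is that both arms are filtered.
- **The number of VLs is a poor proxy for failure.** Because the study period stops at the endpoint VL, retests after an unsuppressed endpoint VL are not counted. People unsuppressed early who re-suppress have extra tests but are successes.
- **Delays may cluster** by clinic or period, which would weaken the gradient in step 2.

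A reader might infer that the rule drops mostly unsuppressed people and so confirms non-inferiority automatically. The SAP does not support this. It gives none of the inputs, and failures with a missing VL have few results and tend to be kept, which pushes the other way (scenario E).

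What the objection does not remove is the endpoint-VL condition. It falls on every success and not on missing-VL failures, whatever is assumed about retesting. Nor is symmetry between arms assured. Section 4.3 restricts the set to "participants for whom the VITAL intervention was technically successful", wording with no clear meaning in a control clinic, and endpoint 9 looks for a between-arm difference in retest timing.

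**Conclusion.** The point holds in a limited form. Inclusion in the per-protocol set depends on the outcome, partly through a result whose return time is irrelevant to the endpoint. How the rule works in control clinics, and for people with no VL, should be stated. The endpoint-VL condition alone could move an OR of 0.80 to between 0.73 and 0.67, if 20% of results are late in the intervention arm, the control arm is not filtered, and 40% to 80% of failures lack an endpoint VL. Extra tests among unsuppressed failures could move it upwards instead. The size and sign depend on quantities that the SAP does not give, and there is no bias in the OR if the arms behave alike. The primary ITT conclusion is unaffected. The consequence is for interpretation: this analysis, as defined, can neither confirm nor challenge non-inferiority.

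**What to change.** In SAP 4.3, 6.1, Table 3 and 6.2:

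1. Base the 31-day rule only on VLs drawn before the endpoint VL or, if there is none, before the 24-month window opens.
2. Apply it identically in both arms and name the data source. Figure 1 lists the VL database review without the intervention-only mark, so a common source is plausible, but the SAP does not say that it records when results arrived.
3. Keep participants with no earlier VL in the set, with a missing endpoint VL counted as failure.
4. Report the number excluded by arm and by outcome.
5. State that agreement with ITT is not confirmation of non-inferiority, because the set is still selected after randomisation.

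The change removes the step 1 distortion and returns scenario E to 0.80, since one earlier test is then judged for everyone. It does not remove selection by number of earlier tests. In scenario C the ratio at r = 0.80 stays 0.80/0.512 = 1.5625. In D, where the two effects had offset each other, it becomes 0.80/(0.5 × 0.80 + 0.5 × 0.512) = 1.22, so the OR would be 0.98 if control clinics were still unfiltered. That is why items 2, 4 and 5 belong with item 1. Judging only the first VL would remove this remainder, but would ignore the later delays that the analysis is meant to examine.

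The cost is some wording and one derived variable, and a late endpoint result no longer excludes anyone. SAP 1.4 dates version 1.1 during analysis, so the change should be logged as made at that stage, with the set as now defined reported alongside.

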- We added a sensitivity analysis for the primary endpoint using imputation for VLs missing at 24 months in the ITT population.
- We added a sensitivity analysis for the primary endpoint in a per-protocol population including participants for whom all viral loads were available in the VITALapp ≤31 days after phlebotomy.

Primary endpoint	Population	Comparison
Proportion of participants engaged in care	ITT	i. Non-inferiority
(defined as documented visit attendance) with documented viral suppression (< 50 copies/mL) 24 months (16-28 months) after enrollment*		ii. Superiority

Sensitivity analysis for the primary endpoint

1.	Proportion of participants engaged in care	ITT	13.:
	(defined as documented visit attendance)		i. Non-inferiority
	with documented viral suppression (<1000 copies/mL) 24 months (16-28 months) after enrollment		ii. Superiority

 Proportion of participants engaged in care (defined as documented visit attendance) with documented viral suppression (<50 copies/mL) 24 months (16-28 months) after enrollment ITT using imputation for VLs missing at 24 months

PP*

 Proportion of participants engaged in care (defined as documented visit attendance) with documented viral suppression (<50 copies/mL) 24 months (16-28 months) after enrollment

4.	Proportion of participants with viral re-	ITT	45. hierarchical (i.e. 4.
	suppression (< 50 copies/mL) 24 months (16-		only if the primary
	28 months) after enrollment among all		endpoint is non-inferior,
	participants with an unsuppressed VL (≥ 50		and 5. only if 4 is
	copies/mL) during the first 12 months of		superior):
	follow-up		Superiority
	•		, ,
5.	Proportion of participants with sustained	ITT	
	viral suppression (defined as >1 VL <50		
	copies/mL) during 24 months follow-up		
	ondary endpoints indicative of clinical		
ber 6.	nefit or harm Rate of mortality at 12 and 24 months after	ITT	67.: Equivalence
٠.	enrollment		8.: Superiority
			on superiority
7.	Proportion of participants with confirmed TB		
	diagnosis at 12 and 24 months after		
	enrollment		
8.	Disengagement from care at 12 and 24		
	months after enrollment		
	ondary endpoints expressing supportive		
	dence Time to follow-up VL in case of an	ITT	913.: Superiority (for 9
9.	unsuppressed VL (≥ 50 copies/mL)	111	11. the upper bound of
	unsuppressed vi (2 30 copies/inii)		the 95% CI must be below
10	Time to ART regimen adaption in case of		1, and for 1213. the
10.	virologic failure**		lower bound of the 95% C

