Primary outcome: For the analysis of the primary outcome, we will use a multi-level logistic regression model including clinic cluster as a random effect, arm allocation and the randomization stratification factor (district) as a fixed effect. Unavailability of a viral load or only an invalid viral load result in the predefined primary endpoint window (for any reason) will be considered as failure. Results will be reported as adjusted odds ratios and absolute differences with confidence intervals. For the primary endpoint, non-inferiority in the ITT population and superiority in ITT will be assessed but no statistical multiplicity adjustment will be needed because of the closed testing principle. For the non-inferiority comparison, a confidence interval approach will be used. Under the assumptions of the sample size calculation, non-inferiority is compatible with the lower bound of the one-sided 97.5% confidence interval for the adjusted odds ratio for the primary outcome exceeding 0.8. A figure illustrating the confidence interval and the non-inferiority margin will be presented. If the non-inferiority is established, then we will assess for superiority by assessing whether the two-sided 95% confidence interval of the adjusted odds ratio excludes 1.

Assessment of cost (primary outcome): We will analyse cost-effectiveness if the intervention is found to be superior or assess the budget impact if the intervention is found to be non-inferior. For the cost-effectiveness analysis, we will use the primary endpoint and mathematical models of HIV transmission. Costing data will include: (1) conversion rate of local currency to U.S. dollars at 6-month intervals over the life of the project; (2) costs of all commodities used in the intervention; (3) average time clients spent with intervention including transportation, (4) staff time and representative salaries; (5) local average wages of the target population; (6) remunerations to clinics; and (7) other relevant costs, including training of providers and transport costs.

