Effect modification (primary outcome): For effect modification of the primary outcome the following variables will be considered:

- i. Age groups (18-24, 25-39, 40-59, and ≥60 years)
- ii. Gender (female, male)
- iii. Cell phone access (yes, no)

Analyses will be performed as for the main primary outcome analysis including an interaction term between these potential effect modifiers and the randomized group. If an interaction term is found to be significant (p-value<0.05), effect estimates will be summarized descriptively by subgroup categories. As the study is not powered for these pre-planned subgroup analyses, no formal hypothesis testing will be done.

Secondary endpoints which may become the basis for additional claims: In case non-inferiority of the primary endpoint is established, these will be evaluated hierarchically.

- 4. Proportion of participants with viral re-suppression (<50 copies/mL) 24 months (16-28 months) after enrollment among all participants with an unsuppressed VL (≥ 50 copies/mL) during the first 12 months of follow-up: This analysis will include individuals with a VL ≥50 copies/mL in the first 12 study months and then directly follow the primary endpoint analysis.
- 5. Proportion of participants with sustained viral suppression (defined as >1 VL <50 copies/mL) during 24 months follow-up: This analysis will directly follow the primary endpoint analysis with endpoint adapted to sustained viral suppression <50 copies/mL throughout the study. Sustained viral suppression is defined as >1 VL <50 copies/mL from study start to end of 24-month window (0-28 months) along with no VL ≥50 copies/mL.

Secondary endpoints indicative of clinical benefit or harm: These will be evaluated independently of the primary objective and without hierarchy / multiplicity adjustment.

- 6. **Rate of mortality at 12 and 24 months after enrollment:** This analysis will use Cox regression adjusted for clinic and district by study arm.
- 7. **Proportion of participants with confirmed TB diagnosis at 12 and 24 months after enrollment:** This analysis will directly follow the primary endpoint analysis with endpoint TB diagnosis (window: 0 months to primary endpoint or 28 months).
- 8. **Disengagement from care at 12 and 24 months after enrollment:** This analysis will directly follow the primary endpoint analysis with endpoint disengagement from care at 24 months, defined as neither a documented visit attendance nor a VL measurement (window: 16-28 months).

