6.3. Missing data

Where applicable, percentages will be of non-missing values, with the number (%) of missing values reported separately.

As detailed in section **6.2**, main analyses of the primary outcome will include all participants as randomized with missing data counted as failures. No missing covariates are expected as the analysis only includes arm, stratification factor district and cluster. There will be a sensitivity analysis assessing the effect of imputing missing viral loads in the primary endpoint window.

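### Endpoint 5 (sustained suppression) requires no viral load in months 16-28, so a participant with two early suppressed results and no later test counts as a success

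*SAP*

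**What the plan says.** Section 6.2 gives the aim of endpoint 5 as the primary analysis "with endpoint adapted to sustained viral suppression <50 copies/mL throughout the study". It then gives the rule: "defined as >1 VL <50 copies/mL from study start to end of 24-month window (0-28 months) along with no VL ≥50 copies/mL". The rule sets no minimum spacing between results and does not require a result in the 24-month window (months 16-28), attendance in that window, or survival to it. Table 3 in section 6.1 carries only the short form, "viral suppression (defined as >1 VL <50" copies/mL, without the condition on results of 50 or more.

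For the primary endpoint, section 6.2 says that a missing or invalid viral load "in the predefined primary endpoint window (for any reason) will be considered as failure". Section 6.3 states that rule for the primary outcome: "main analyses of the primary outcome will include all participants as randomized with missing data counted as failures".

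Table 3 and section 6.2 place endpoint 5 among the secondary endpoints that may support additional claims. It is tested for superiority, and only if the primary endpoint is non-inferior and endpoint 4 is superior.

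**The concern.** The label promises durability over 24 months, but the rule can be satisfied well before month 16. After that, the absence of further results is read in the participant's favour: with no later test there can be no result of 50 or more. Someone who dies or is lost after two good results is thus a failure on the primary endpoint, disengaged under endpoint 8 (no visit and no viral load in months 16-28), and a success on sustained suppression.

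This is a stated rule that gives the wrong class, not a detail left open. What is at stake is the meaning of a confirmatory claim. A superiority statement on sustained suppression would rest partly on participants whose status in the second year is unknown or who have died.

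**Working it through.** The point rests on no stated sample size, power or error rate, so there is no figure of the plan to reproduce for it. The check applies the written rules to example participants.

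**Rules used**
- Endpoint 5, section 6.2: at least two viral loads <50 in months 0-28 and none ≥50.
- Endpoint 5, Table 3 short form: at least two viral loads <50.
- Primary endpoint, sections 3.7 and 6.2: the viral load closest to month 24 within months 16-28 is <50; none in the window is failure. Visit attendance is taken as documented for those tested in the window.
- Corrected rule: the section 6.2 rule plus a viral load <50 in months 16-28.

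| Profile | Section 6.2 | Table 3 short form | Primary | Corrected |
|---|---|---|---|---|
| <50 at months 0 and 6, lost at month 8 | success | success | failure | failure |
| <50 at months 1 and 9, died at month 11 | success | success | failure | failure |
| <50 at months 0, 12 and 24 | success | success | success | success |
| <50 at months 0 and 12, 400 at month 24 | failure | success | failure | failure |
| Single result, <50 at month 24 | failure | failure | success | failure |

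The first two rows are the problem.

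**Who is affected.** Under section 6.2 any result in months 16-28 of an endpoint 5 success must already be <50. The current and corrected rules can therefore differ only for participants with no valid viral load in the window, at least two earlier results <50 and none ≥50. Hence

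share affected = P(no viral load in 16-28) × P(two earlier results <50, none ≥50 | no viral load in 16-28).

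The SAP gives neither factor. With assumed ranges of 5-30% and 20-80%:
- low: 0.05 × 0.20 = 0.01
- middle: 0.10 × 0.50 = 0.05
- high: 0.30 × 0.80 = 0.24

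This is 1 to 24 points of all participants, with 5 points at the middle values. It is a share of both arms together and says nothing about the difference between them.

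**Does another part of the SAP close the gap?** Endpoint 5 is said to follow the primary analysis directly, which might import the missing-is-failure rule. Three things speak against it:
- That rule is tied to the primary endpoint's window and, in section 6.3, to the primary outcome. Endpoint 5 has its own definition and a 0-28 month window.
- The same instruction is given for tuberculosis ("This analysis will directly follow the primary endpoint analysis with endpoint TB diagnosis"), ART modification and TPT, where failure for a missing viral load has no meaning. It most naturally refers to the regression model.
- The general study-period rule does not remove these participants either: it runs "until 28 months after enrolment if endpoint VL missing as study period for each participant", so an untested participant is carried to month 28 with nothing on record against them.

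**The case against.** The strongest reply is the gatekeeping. Endpoint 5 is reached only after primary non-inferiority, where no result in months 16-28 is a failure, and after superiority on endpoint 4, which needs re-suppression in the same window. Both steps penalise loss. Mortality and disengagement are also analysed by arm outside the hierarchy, and the flowchart shows disengagement and withdrawal by group. This stands and narrows the risk of a false claim. It does not remove it. The margin tolerates about 5 points: at 65% in the control arm the odds are 0.65/0.35 = 1.857; × 0.8 = 1.486; 1.486/2.486 = 59.8%, a gap of 5.2 points. Endpoint 4 covers only participants with a result ≥50 in the first 12 months, none of whom can succeed on endpoint 5 under section 6.2, so that step does not examine the misclassified group.

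A reader might infer three stronger things that the SAP does not support:
- **That the error favours the intervention.** Section 2.1 describes care differentiated by previous results, but the SAP states no different testing schedule for suppressed participants. The one comparison of viral load timing, endpoint 9, starts from a result ≥50, and those participants already fail endpoint 5.
- **That the rule rewards leaving care.** Loss after two good results removes the risk of a disqualifying one, but loss before the second result is a failure. The net direction cannot be derived.
- **That Table 3 is a rival definition.** Section 6.1 calls the table an overview, and the item heading in section 6.2 uses the same short form before giving the full rule. It is an abbreviated label, though on its own it would let the rebound profile in the fourth row count as sustained.

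**Conclusion.** The point holds as a matter of definition. Under the rule in section 6.2, participants with two early suppressed results and no viral load in months 16-28, whether through death, loss or lack of testing, count as successes on sustained suppression while failing the primary endpoint. No assumption is needed for that.

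The size is not known: the 1 to 24 point range depends wholly on the assumed inputs, and it includes people still in care but untested as well as those who died or left. No between-arm bias, and no direction for one, can be claimed from the document. Since this is the last confirmatory step behind two gates, it should be corrected, but it does not touch the primary conclusion.

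**What to change.** Define success on endpoint 5 as more than one viral load <50 copies/mL in months 0-28, including the endpoint viral load <50 in the 24-month window (months 16-28, the same measurement as in the primary analysis), with no viral load ≥50 at any time in months 0-28. State that death, loss or no valid viral load in months 16-28 is a failure. Put this full definition in Table 3 as well as section 6.2.

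The bar on results ≥50 should stay across the whole of months 0-28. Applying it only between a 12-month and a 24-month result would loosen the rule: 400 copies/mL at month 3 followed by <50 at months 12 and 24 fails now and would then pass.

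Section 1.4 records that V1.1 was revised during analysis, so this would be a late change to a claim-bearing endpoint. Log it with its reason and timing, and report the result under the current definition alongside.

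The cost is SAP wording and one additional derived variable from viral load results and dates already collected. The corrected success group is a subset of the current one, so expect a lower success proportion in both arms; it cannot rise in either.
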